Form Type	Data Collection Method	Measure	Baseline	Baseline Re-assess	Weekly	Week 4	Mid-Treatment Assess (wk 6)	Post-Treatment Assess (wk 12)	3-month Follow-up	12-month Follow-up
Diagnosis & Screening	Paper/PDF/REDCap	MINI	x							
	REDCap	Demographics	x							
	REDCap	Treatment History	x							
	REDCap	Treatment History	x							
	REDCap	Treatment History	x							
	REDCap	Lifetime Meds	x							
OCD & Related Symptoms	Paper/PDF/REDCap	Y-BOCS	x	x			x	x	x	x
	REDCap	OCSRS	x				x	x	x	x
	REDCap	QIDS-SR	x	x			x	x	x	x
	App/ REDCap	PHQ-2			x					
	App/ REDCap	Suicide item			x					
	REDCap	C-SSRS: Lifetime	x							
	REDCap	C-SSRS: Update		x						
	REDCap	CGI-S: Clinician	x	x						
	REDCap	CGI-I: Clinician		x			x	x	x	x
Functioning	App/ REDCap	CGI-I: Patient (OCD)			x			x	x	x
	REDCap	Q-LES-Q	x				x	x	x	x
Safety	REDCap	WSAS	x				x	x	x	x
	REDCap	CONCOM		x			x	x	x	x
	REDCap	Adverse Events Form		x			x	x	x	x
Tx expectancy, motivation,	REDCap	Life Events		x			x	x	x	x
	REDCap	Cred/Expectancy	x				x			
	REDCap	CSQ-8					x	x		
	REDCap	URICA	x							

Form Type	Data Collection Method	Measure	Baseline	Baseline Re-assess	Weekly	Week 4	Mid-Treatment Assess (wk 6)	Post-Treatment Assess (wk 12)	3-month Follow-up	12-month Follow-up
satisfaction, feedback	REDCap	TUQ - App†	x				x	x	x	
	REDCap	TUQ – Website*	x				x	x	x	
	REDCap	App Feedback†	x				x	x		
	REDCap	Website Feedback*						x		
	REDCap	Technologist							x	
	REDCap	uMARS†						x		
Neurocognitive	REDCap/Inquist	Stroop	x			x		x		
	REDCap/Inquist	WCST	x			x		x		
COVID	REDCap	COVID Impact	x				x	x	x	x
	REDCap	GAD-7 with COVID	x				x	x	x	x
	REDCap	Substance Use	x				x	x	x	x
Other	Beiwe	Wifi check-in question			x					
	REDCap	Self-Help Questionnaire	x				x	x	x	x

† Only included for participants in the CBT app condition

* Only included for participants in the HealthWatch condition

If more than ten days elapse between a patient's initial baseline screening assessment and the start of treatment, the study IE would re-administer select forms, including an additional Y-BOCS and QIDS-SR form.

Despite our best efforts to retain participants, we do expect dropouts. Except for subjects who withdraw consent to participate, all who are withdrawn or drop out of the study will be asked to complete all scheduled assessments and we will provide renumeration for participation in assessments

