Phone Usage Patterns: Dynamics of the phone usage provides an additional insight into clinically relevant changes to a person's mental health status. For that reason, Beiwe will collect phone-unlock events and data traffic to characterize patterns and quantify daily phone and internet usage. Note that the data traffic refers only to the periodically sampled number of bytes sent and received, and it does not include any sensitive information such as internet history or the names of the installed applications. Beiwe may also monitor how much the participant uses their phone for calling and texting and keep track of the people they communicate with. To encourage occasional interaction with the Beiwe app, we will administer a weekly survey question to participants via Beiwe (Wifi check-in question). For details on how this information will be stored and anonymized please see "Privacy and Confidentiality" below.

However, sampling raw GPS location coordinates may intrude on one's privacy. To protect privacy of the study participants, we will apply the following procedure. The location coordinates will be first collected at the secured server located at the hospital or locally on the phone. We will subsequently remove the raw location coordinates by replacing them with randomly generated strings as location labels (such as "ghhu45", "235oh4", "8n8hj3", ...), where each unique location in the dataset will correspond to a unique de-identified label. This will allow us to quantify mobility of the participants without requiring us to store actual geographical locations in the long-term. In addition to location, other sensor data collected by the participant's Smartphone may be used to quantify mobility, including accelerometer, steps, calories burnt, and sedentary time.

Application Usage Metrics: To improve the usability of the application, usage metrics may be collected (for example operating system version and device model, time and date when the application is opened or closed, time spent on each page visited, notification timing, etc). Additionally, we may collect user's battery status and charging patterns, and network traffic (e.g., number of bytes sent/received, and the hashed Wi-Fi-antenna indicator). These metrics will be stored in the same fashion as passive sensor data and user survey responses collected via the app.

B. Drugs to be used

Not applicable

C. Devices to be used

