Baseline differences between the treatment arms in demographic and other potential prognostic variables will be examined using chi-square analyses for discrete variables (if prevalence >10 in the treatment arm with the lower prevalence, or Fisher’s exact test if not) and t-tests for continuous variables. Prior to data analysis, all major variables will be screened for inconsistent or abnormal values. Continuous measures will be assessed for skewness and outliers (based on model residuals), and, if needed, will be transformed to better meet modeling assumptions of normality and homogeneity of variance. A two-tailed p-value $<.05$ will be considered evidence of statistical significance for the primary and secondary outcomes. Our primary and secondary analyses will use generalized linear mixed-effects models (GLMMs). GLMMs can easily accommodate nesting of repeated observations within subjects, include all who complete at least one assessment (including the baseline assessment), and are the preferred method to analyze longitudinal data (Hamer and Simpson, 2009). Despite our best efforts to retain participants, we do expect dropouts (subjects who are lost to follow-up or withdraw early from the study). We will attempt to perform all scheduled assessments for subjects who are withdrawn from the protocol and will provide financial incentives for participation in assessments. Our intent-to-treat sample will include all randomized patients who complete at least one assessment, making our

primary and secondary analyses intent-to-treat analyses. We will also perform “per protocol” analyses. Our per protocol population will include all randomized patients who complete the baseline and post-treatment assessments, and who did not initiate prohibited treatment during the study. We will repeat our GLMM analyses using the per protocol sample. Dropout, study withdrawal, and loss to follow-up will be tabulated by reason and treatment arm. Analyses will be conducted to ascertain to what extent dropouts are nonrandom, and, if so, what factors are associated with dropout. To evaluate potential attrition bias, study dropouts will be compared to study completers.

A. Specific data variables being collected for the study (e.g., data collection sheets)

Specific variables being collected and their timeline are presented above, in Tables 1 and 2, and described in the Study Procedures section.

B. Study endpoints

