The primary outcome model will be a hierarchical mixed model (i.e., GLMM) that will include time (categorical; baseline, mid-point, and end-of-treatment), treatment (app-CBT vs. supportive attentional control), and their interaction as fixed effects, and will model time as a repeated measure using either an autoregressive (AR1), Toeplitz, compound symmetry, or unstructured covariance matrix, based on best fit determined by AIC and BIC. The unstructured covariance matrix model will only be used if this model fits significantly better than alternative simpler models, based on -2 log likelihoods. The main hypothesis test will be based on a specific contrast of treatment difference at week 12. Because these analyses will include all subjects who are randomized and complete at least one assessment, it is an intent-to-treat analysis. These analyses will include only the 3 assessments from baseline to post-treatment and will not include the 3-month or 12-month follow-up (FU) assessments, because treatment response could be affected by subjects seeking other treatments during the FU period. Between-group effect sizes will be calculated using Cohen's *d*. This analysis will then be repeated using the per-protocol sample.

In addition to the analyses specified above, we will describe the proportion of subjects in each treatment arm who achieve response, where response is defined as a 25% or greater reduction in Y-BOCS score from baseline to end of treatment (week 12) (Storch et al., 2006). While no formal comparisons will be made between treatments, the reporting of response rates is clinically useful and will facilitate comparison to other studies in the field. We will report response as observed (excluding subjects with missing data at week 12) and will additionally examine how rates may change when a) applying a last observation carried forward approach, and b) conservatively considering subjects with missing week 12 scores as non-responders.

Secondary endpoint: Difference in secondary clinical outcomes (i.e., QIDS-SR, WSAS, Q-LES-Q-SF) at the end of treatment (i.e., preliminary efficacy for secondary symptoms)

Analysis:

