We will use the same hierarchical mixed modeling approach as described for the primary endpoint to examine significant differences in secondary outcome measures (i.e., depression severity (H2.1), functional impairment (H2.2), and quality of life (H2.3)) at post-treatment between participant in the app-CBT vs. supportive attentional control conditions. We will not adjust for multiple testing among secondary outcomes based on the recommendation of Cook and Farewell (1996), who argue that multiplicity adjustments are not necessary if separate test results are interpreted marginally and address different aspects of the patient experience and decision-making process rather than alternative assessments of efficacy.

Exploratory endpoint 1: Assess feasibility and acceptability

Analysis:

We will test feasibility and acceptability by examining:

- H3.1: Refusal and dropout rates and reasons, by group: Drop-out rates by treatment (app-CBT vs. supportive attentional control) will be compared using logistic regression. Drop-outs will be defined operationally as participants who do not complete either an endpoint or follow-up assessment of the primary outcome measures (Y-BOCS), as well as participants in the CBT arm who do not use the app or participants in the HealthWatch arm who do not use the website at least once between assessments (i.e., at least once between baseline and week 6 and at least once between week 6 and week 12). We will use one-tailed tests to examine if the odds of drop-out in the app-CBT group are higher; if non-significant, we will interpret the results as an indication that the app-CBT treatment is feasible in comparison to the supportive attentional control condition; conversely, significantly higher odds of drop-out in the app-CBT condition would indicate a lack of feasibility.

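### The per-protocol set has no condition on using the assigned app or website, so some participants counted as drop-outs under H3.1 are analysed as per protocol

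*Combined protocol and SAP*

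**What the plan says.** **Per-protocol set.** The opening text of section VI (Biostatistical Analyses) says the set will "include all randomized patients who complete the baseline and post-treatment assessments, and who did not initiate prohibited treatment during the study". It adds: "We will repeat our GLMM analyses using the per protocol sample". Section VI.C says of the primary Y-BOCS model: "This analysis will then be repeated using the per-protocol sample".

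**Drop-out under H3.1.** Section VI.C, Exploratory endpoint 1, gives two routes to drop-out. One is a missed Y-BOCS assessment. The other is non-use: "participants in the CBT arm who do not use the app or participants in the HealthWatch arm who do not use the website", where the use required is "at least once between baseline and week 6 and at least once between week 6 and week 12".

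**Drop-out elsewhere.** The opening text of section VI speaks instead of "dropouts (subjects who are lost to follow-up or withdraw early from the study"), with no reference to use.

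**Assessment after drop-out.** The note under the Measures Chart states that, apart from those who withdraw consent, "all who are withdrawn or drop out of the study will be asked to complete all scheduled assessments", with payment. Section VI says much the same of withdrawn participants.

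**Records of use.** Under Application Usage Metrics, the app may log such items as "time and date when the application is opened or closed, time spent on each page visited". Item 5b of Privacy and Confidentiality says the control site keeps only a study identifier, the survey week and whether that survey was completed. The Measures Chart schedules a self-report utilization questionnaire, in an app and a website version, at weeks 6 and 12 among other visits.

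**The concern.** A per-protocol analysis is usually read as the effect among people who followed the protocol, and receiving the assigned intervention is the main part of that. Here the set removes people who missed week 12 or took outside treatment and keeps people who did not engage with the intervention at all. The plan foresees such people, because it writes non-use into the H3.1 rule, and it works to bring them back for the week-12 visit. The more successful that retention effort is, the more non-users enter the set.

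At stake is the meaning of a supportive result. Non-users in the app arm would tend to pull the per-protocol estimate toward the intent-to-treat estimate. If the two agreed, a reader could take this as confirmation when the agreement is partly built into the definition.

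**Working it through.** **1. The definitions side by side.** Each participant below attends baseline and week 12 and starts no prohibited treatment.

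| Participant | H3.1 (section VI.C) | Per-protocol set (section VI) |
|---|---|---|
| Uses the app or website in both intervals | Not a drop-out by the non-use route | Included |
| Uses it before week 6 only | Drop-out | Included |
| Uses it after week 6 only | Drop-out | Included |
| Never uses it | Drop-out | Included |
| Withdrawn at week 8, used it in both intervals | Not a drop-out by the non-use route | Included |

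Rows two to four are the conflict. It is not confined to people who never open the programme, since missing either interval is enough under H3.1. No other section adds a use condition to the per-protocol set.

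**2. The plan's sample size.** Inputs from section VI.D: difference 0.76, SD 1.1, two-sided alpha 0.05, power 0.90, 1:1 allocation, drop-out 20%.

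- A two-sample t-test with standardized difference 0.76/1.1 = 0.691 needs 45.006 per arm, rounded up to 46.
- Allowing for drop-out: 46/0.80 = 57.5, rounded up to 58 per arm, or 116 in total. This matches the plan.

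The per-protocol definition plays no part in this calculation.

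**3. Illustration of dilution.** Let f be the fraction of the app arm's per-protocol set that fails the use rule. Assume that these people gain nothing, that adequate users gain the planned 0.76, and that website non-use does not shift the control mean. Then

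expected per-protocol difference = 0.76 × (1 − f).

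- f = 10%: 0.76 × 0.90 = 0.684, or 0.68.
- f = 20%: 0.76 × 0.80 = 0.608, or 0.61.

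**4. What this would do to the per-protocol comparison.** With 120 randomised and 20% lost, the set has 120 × 0.80/2 = 48 per arm. Two-sample t-test power at SD 1.1, under the same assumptions:

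| f (assumed) | Present set, 48 per arm | Users only, same fraction removed from each arm |
|---|---|---|
| 0% | difference 0.76, power 92% | 48 per arm, power 92% |
| 10% | difference 0.68, power 85% | 43 per arm, power 89% |
| 20% | difference 0.61, power 76% | 38 per arm, power 84% |

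The values of f are not from the documents. The definitional conflict in step 1 does not depend on them.

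**The case against.** **The H3.1 rule serves one exploratory feasibility endpoint.** An analysis set may be defined differently, and the treatment is self-paced with no stated minimum dose. This stands in part. The per-protocol rule is explicit and pre-specified, and some use threshold is a choice. But the plan has already chosen one for this trial, and a set that admits people who received none of the intervention does not match its label.

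**The primary and secondary tests are intent-to-treat, and non-use is not hidden.** H3.1 compares drop-out, including non-use, between arms, and H3.3 describes app use. This stands in full and limits the weight of the point. Nor does the plan say that agreement between the two analyses will be presented as robustness; that is a risk in how a reader interprets it.

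**The dilution figures are extreme.** This stands. People who used the app up to week 6 and then stopped may well have benefited, so zero benefit in everyone failing the rule is a worst case among assumptions of no harm. The planned 0.76 may also not be the effect in adequate users.

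**Use is recorded differently in the two arms.** This stands. A control participant who reads a module but completes no survey leaves no stored record, while an app opening may be logged. A use rule without a named source could exclude people unequally by arm.

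**A stronger reading about withdrawal.** A reader might infer that anyone withdrawn early who attends week 12 is also an H3.1 drop-out wrongly kept in the set. The documents do not support this. H3.1 has no withdrawal criterion, as the last row of the first table shows. Nor would it be sound to remove everyone withdrawn before week 12. Items 5 and 7 of Minimizing of Risks and Safety Reporting allow withdrawal for clinical deterioration or need for more care, so that exclusion would select on poor outcome.

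**Conclusion.** The point holds as a problem of definition and labelling in a supportive analysis. Participants who miss the plan's own minimum use in one or both intervals can be H3.1 drop-outs and per-protocol cases at once, in the repeated primary and secondary models. This follows from the text and needs no assumption.

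The expected direction is dilution toward the intent-to-treat estimate. Its size cannot be determined from the documents. The figures of 0.68 and 0.61 are worst cases that rest on an assumed f, no benefit in any non-user, and 0.76 as the effect in users.

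A reader might go further and infer that the primary efficacy result is biased or the trial underpowered. Neither follows: the primary and secondary tests use the intent-to-treat sample, and the 116 reproduces without reference to the per-protocol set. The change is worth making before outcome data are seen by arm, but it is not critical.

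**What to change.** 1. **Add a use condition.** In section VI, require for the per-protocol set, in both arms, at least one use of the assigned app or website in each H3.1 interval, alongside the two existing conditions.
2. **Name the data source for each arm and make the two comparable.** Options already in the protocol are the utilization questionnaire at weeks 6 and 12, the same instrument in both arms though self-reported, or logged openings for the app with weekly survey completion for the website. If logs are chosen, state that app openings will be collected, and accept that survey completion is a stricter test than opening the app. Use the same source for H3.1.
3. **Keep the present set under an accurate label**, such as *completers without prohibited treatment*, as a separate supportive analysis.
4. **Do not exclude participants merely because they were withdrawn before week 12.**

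The cost is a few sentences, a decision on use data that H3.1 needs anyway, and a smaller per-protocol set. In the illustration it falls from 48 to 43 or 38 per arm. The set would also be further selected on events after randomisation, so it should stay supportive, with intent-to-treat primary.

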D. Treatment assignment and randomization (if applicable)

Eligible subjects will be randomized to app-based CBT for OCD (Perspectives OCD) or to a supportive attentional control condition (HealthWatch) (50/50 chance). Randomization will be stratified by participants' medication status, in order to evenly distribute any potential medication effects on treatment response across both study arms. Participants in both conditions will be assessed at regular intervals (see Table 2 below). The duration of the supportive attentional control condition will be the same for participants who are treated with CBT. The supportive attentional control group will allow us to determine if active treatment is superior to a psychoeducational website focusing on general health and well-being.

Supportive Attentional Control: To maximize the validity of our study, we will match the duration of the supportive attentional control condition to that of the CBT condition (i.e., approximately 12 weeks). Modules on the supportive attentional control website (HealthWatch) will be made available to participants in parallel to the modules being unlocked on the app in the CBT condition. To protect the safety of participants assigned to the supportive attentional control condition, participants who have active suicidal ideation at the screening assessment (see Inclusion/Exclusion Criteria) will not be eligible to participate. The supportive attentional control website (HealthWatch) provides brief psychoeducational content on OCD and general well-being (e.g., nutrition, heart health), but does not specifically target symptoms of OCD. We will offer referral resources to study candidates who do not wish to be randomly assigned to a possible inactive condition.

STUDY PROCEDURES

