Screening/Assessment Calls and Randomization Procedures: The screening visit will take place over a HIPAA-compliant video conference call (or phone call) and will last approximately 2-3 hours (including an additional hour over the computer for self-report assessments). Subjects will first provide electronic informed consent with the IE, or Drs. [name], [name], or [name] (see Section C, “Procedures for obtaining informed consent” for further details). They will then be assessed by the IE for eligibility, using the below assessment instruments (see Table 2), including a structured diagnostic interview, clinician-rated measures, and self-report measures. Baseline severity and symptom data will also be obtained, using the below assessment instruments. Participants will complete self-report questionnaires via REDCap, online. If an enrolled participant has already completed the same clinician-administered and self-report questionnaires within the past six months as part of a different study within the Center for OCD and Related Disorders, they may be able to consent to give us permission to access data from their previous screening assessment. After the Screening/Baseline visit, participants will be notified by study staff via e-mail (see appendix) regarding their eligibility status, and they will be given the opportunity to discuss this further with our study staff by phone. If eligible, participants will then complete the rest of the self-report tasks and the optional neurocognitive computer tasks (i.e., Stroop Task, Wisconsin Card Sorting Task, below), using the same procedures that were previously approved in Protocol #2017P000293. Ineligible participants will be provided with treatment referrals and resources. When screened patients do not qualify for or choose not to participate in the study, reasons will be documented. Eligible subjects will be randomized through a secure REDCap randomization database in a 1:1 ratio to app-based CBT for OCD or a supportive attentional control condition, stratified by medication status. Those beginning the CBT treatment will be taught to download the app and those beginning the HealthWatch condition will be taught how to access the website. Both groups will receive instruction in downloading the Beiwe app, which was previously approved for use in Protocol # 2019P002041. Please see the schedule of assessments and measures administered at each time point in Table 2. These assessment lengths are similar to those used in other studies in our program and have been well-tolerated by participants. Participants will complete Stroop and Wisconsin Card Sorting neurocognitive computer tasks at home after 4 weeks and at the end of treatment assessment. To avoid dropout, participants will be paid \$25 for completing the week 4 neurocognitive tasks, mid-treatment visit, end-treatment visit, and 3-month follow up assessments and \$50 for the 12-month follow-up.

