We will use hierarchical mixed models similar to the ones used for the primary and secondary outcome analyses, but will add follow-up assessments (i.e., 3-month and 12-month) to the data as additional time-points. We will then use specific contrasts (for each outcome model) to test for significant treatment group differences at the 12-month follow-up time-point. In the case that at least 10% of the participants who completed the end-of-treatment assessment initiated additional or subsequent evidence-based treatment for OCD at clinically relevant dosage (for medication) or frequency (for therapy), we will conduct a sensitivity analysis for this aim using treatment (yes/no) as a time-varying covariate in the model to account for the potential effect of outside treatment. In this context, ‘evidence-based’ treatments will be operationally defined to include any psychosocial or medication treatments indicated for OCD or closely related anxiety disorders that have shown efficacy in prior clinical trials, and ‘clinically relevant dosage’ will be evaluated by psychiatrists or psychologists in our treatment program who specialize in OCD or related disorders. In addition, we will also add descriptive stats about how many participants are responders at both end-of-treatment and 12-month follow-up, how many participants are new responders by the 12-month follow-up, how many participants are no longer considered responders at the 12-month follow-up, and how many participants were not considered responders at either assessment. No formal comparisons will be made between treatments in these numbers.

Exploratory endpoint 3: Treatment utilization for OCD concerns following the 3-month follow-up.

Analysis:

We will use logistic regression analysis to examine whether the likelihood of seeking further treatment for OCD during the treatment or follow-up phases (overall, combined) differs between participants who were assigned to the app-CBT and those assigned to the supportive attentional control condition. For this analysis, we will operationally define “treatment utilization” as any indication of participants seeking treatment for OCD during or following the treatment phase, regardless of whether the treatments sought are pharmacological or therapy-based, at sufficient or insufficient dosage/frequency, or considered evidence-based or not.

D. Power analysis

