The sample size required to test a significant treatment response difference between the app-CBT and the control condition at the end of treatment is n=116 (n=58 per group). The sample size estimate is based on a single degree of freedom contrast in an ANOVA design, implemented in SAS for Windows version 9.4. The power model used a two-sided alpha=0.05, a power of 0.90, equal allocation of participants into both treatment arms, an assumption of an effect size of 0.76 comparing the two treatments at the end of treatment, as well as an assumption of a standard deviation of 1.1. The anticipated effect size of the app-CBT was conservatively based on the 95% lower confidence limit of the mean between-group effect size of CBT vs. psychological placebos reported in Ost et al. (g=1.29, 95% CI: [0.76–1.81]; Öst, Havnen, Hansen, & Kvale, 2015). We chose this conservative limit, because the effect sizes of recent, large RCTs of CBT or iCBT vs. various psychological control conditions have been quite variable, ranging from a high of d=1.12 in a comparison of iCBT against online non-directive supportive therapy (n=101; E.

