Andersson et al., 2012) to $d=0.55$ in a trial of iCBT vs. internet-based progressive relaxation therapy (n=179; Kyrios et al., 2018) and $d=0.52$ in a trial of CBT vs. stress management training (n=73; Whittal, Woody, McLean, Rachman, & Robichaud, 2010). In the process of evaluating effect sizes from previous trials, we did not differentiate between internet-delivered CBT and face-to-face CBT, because a meta-analysis including 13 RCTs that directly compared these two treatment modalities in patients with various psychiatric and somatic conditions (total N=1053) showed a pooled effect size (Hedges' g) at post-treatment of -0.01 (95% CI: -0.13 to 0.12; G. Andersson, Cuijpers, Carlbring, Riper, & Hedman, 2014); of note, though, this direct comparison has not been done in trials with patients with OCD. Furthermore, in the wake of the COVID-19 pandemic, various negative mental health states and stressors – including anxiety, worry, depression, loneliness, financial strain, and trauma symptoms – have increased in the US population (e.g., Fowers & Wan, 2020). The variability of these negative mental health states and stressors will likely be higher than during non-pandemic times as multiple waves of the pandemic and state-wide measures of social interaction restrictions sweep the nation in the foreseeable future. In response, we used a standard deviation of 1.1 (instead of the standardized 1.0) in our power calculations to allow for a 10% increase in the variability of symptom severity estimates during the ongoing effects of the COVID-19 pandemic and its socioeconomic aftermath. Lastly, we assumed a conservative drop-out rate of 20% by end of treatment, based on the dropout numbers reported in a meta-analysis of 18 studies targeting self-help treatments for OCD, where studies with self-administered treatment without therapist contact had a drop-out rate of approximately 40%, compared to drop-out rates of 17-20% in treatments with minimal to low therapist contact (Pearcy, Anderson, Egan, & Rees, 2016); the meta-analysis by Ost et al. (2015) reported an estimated dropout rate of 15.5% from in-person CBT treatment.

VII. RISKS AND DISCOMFORTS

A. Complications of surgical and non-surgical procedures

Not applicable

B. Drug side effects and toxicities

Not applicable

C. Device complications/malfunctions

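### Randomisation is stratified by medication status but the primary and secondary models omit it; adding it is a near-free gain in precision

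*Combined protocol and SAP*

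**What the plan says.** Section IV.D (Treatment assignment and randomization) stratifies allocation by "medication status, in order to evenly distribute any potential medication effects on treatment response across both study arms". The randomisation paragraph under Study Procedures repeats it: 1:1 through REDCap to the app or the "supportive attentional control condition, stratified by medication status". Neither place describes blocking within strata.

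Section VI.C, Primary endpoint, lists the fixed effects of the Y-BOCS model as time (three visits), "treatment (app-CBT vs. supportive attentional control), and their interaction as fixed effects, and will model time as a repeated measure". The test is the treatment contrast at week 12. The other analyses inherit this model:

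- Secondary outcomes (QIDS-SR, WSAS, Q-LES-Q-SF): "We will use the same hierarchical mixed modeling approach as described for the primary endpoint".
- Per-protocol analysis (section VI, opening text): "We will repeat our GLMM analyses using the per protocol sample".
- Follow-up (Exploratory endpoint 2): "We will use hierarchical mixed models similar to the ones used for the primary and secondary outcome analyses".

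The one treatment-related covariate named in any outcome model is outside OCD treatment started later. It enters only a conditional sensitivity analysis at follow-up and is not the randomisation stratum.

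**The concern.** The plan treats medication status as possibly prognostic when it allocates participants and then leaves it out when it analyses them. The consequence depends on how allocation is done.

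- **Prognostic, and balanced within strata (for example by blocks).** The design has removed the between-stratum variance from the treatment contrast, but the unadjusted model still counts it as residual variance. The reported standard error is too large and the test rejects less often than its nominal level.
- **Prognostic, but not blocked.** The standard error is right, but the estimate is less precise than it could be.
- **Not prognostic.** Nothing is lost.

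At stake is some precision in the primary contrast and the three secondary contrasts. Bias, inflated type I error and the sample size of 116 are not at issue.

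**Working it through.** **Inputs from the plan (section VI.D).** "The power model used a two-sided alpha=0.05, a power of 0.90, equal allocation of participants into both treatment arms"; effect 0.76; SD 1.1; n = 116 (58 per group); and "we assumed a conservative drop-out rate of 20% by end of treatment".

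**Assumptions, because the documents give no figure.** The share of week-12 variance explained by medication status (R²) is 0, 0.02, 0.05 or 0.10. Half of participants are medicated, with 20% as an alternative. Allocation is either in permuted blocks of 4 within strata or by simple randomisation.

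**Step 1: reproduce the plan's figure.** By the noncentral t, 46 completers per arm are needed (power 0.906). 46 / 0.80 = 57.5, rounded up to 58 per arm, or 116. The stated sample size reproduces.

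**Step 2: what R² means on the plan's scale.** The medicated-versus-unmedicated difference is 1.1 × √(R² / [p(1−p)]). At p = 0.5 this is 0.31, 0.49 and 0.70 for R² = 0.02, 0.05 and 0.10. At p = 0.2 and R² = 0.10 it is 0.87.

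**Step 3: closed form, blocked, no dropout.** The reported standard error exceeds the true one by the factor 1/√(1−R²). For R² = 0.02, 0.05 and 0.10 this is 1.010, 1.026 and 1.054. The true two-sided type I error (t, 90 df) is then 4.8%, 4.4% and 3.9%.

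**Step 4: simulation with dropout.** 116 randomised, 20% random dropout, half medicated, linear model of the week-12 score, 100,000 trials per cell:

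| R² | Blocked: SE overstated | Blocked: type I error, unadjusted | Blocked: power, unadjusted → adjusted | Not blocked: power, unadjusted → adjusted |
|---|---|---|---|---|
| 0 | 0% | 4.9% | 0.908 → 0.907 | 0.906 → 0.902 |
| 0.02 | 0.6% | 4.8% | 0.910 → 0.914 | 0.903 → 0.905 |
| 0.05 | 1.8% | 4.5% | 0.912 → 0.920 | 0.904 → 0.915 |
| 0.10 | 4.1% | 4.1% | 0.915 → 0.932 | 0.904 → 0.929 |

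At R² = 0.10 with blocking, the unadjusted estimate has an empirical SD of 0.2193 and a mean reported SE of 0.2283 (ratio 1.041). Adjusted, these are 0.2171 and 0.2168, and type I error returns to 5.0%. Without blocking, unadjusted type I error is 5.0% throughout. The lowest unadjusted power in any cell is 0.9025. With 20% medicated, the SE overstatement under blocking is nearly the same: 0.7%, 1.6% and 4.3% at R² = 0.02, 0.05 and 0.10.

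**Step 5: main effect or interaction with time?** A three-visit repeated-measures simulation used 60 per arm, 20% missing at week 12, balanced strata, unstructured covariance, assumed visit correlations of 0.5 to 0.65, and 3,000 trials per scenario. Power for the week-12 contrast was:

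| Stratum effect | Omitted | Main effect only | With time interaction |
|---|---|---|---|
| None | 93.2% | 93.2% | 93.2% |
| R² = 0.10 at every visit | 94.1% | 95.2% | 95.3% |
| Zero at baseline, R² = 0.10 at week 12 | 93.9% | 94.6% | 95.3% |

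If the medication effect develops over time, a main effect recovers only about half of the gain. The interaction recovers all of it.

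**Step 6: if the true effect is smaller than planned.** Section VI.D itself cites trials with d = 0.55 and d = 0.52. Putting those values in place of 0.76 (SD 1.1 kept, 46 completers per arm, balanced strata), power at R² = 0.05 to 0.10 goes from 0.66–0.67 to 0.68–0.71 at 0.55. At 0.52 it goes from 0.61–0.62 to 0.63–0.66. The gain is then about 2 to 4 points.

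**The case against.** The strongest reply is that little is at risk. Stratification is there to balance the arms, and it does so whether or not the model adjusts, so the plan does not contradict itself. Power holds at 0.90 without the change.

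The size of the gain also rests on an assumed R². The top value, 0.10, implies a medication difference of 0.70, nearly the whole planned treatment effect of 0.76; with 20% medicated it would be 0.87, which is larger. The eligibility rules already require stable medication for two months and no change during treatment. At R² = 0.02 the gain is only 0.4 points with blocking and 0.2 without.

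Finally, the simulation in step 4 analyses week-12 scores alone with 116 randomised. The planned model keeps dropouts' earlier visits, and the recruitment target is 120.

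Most of this stands as a limit on size. R² = 0.10 should be read as an extreme, and the step 4 powers are not the planned model's exact power. The three-visit simulation starts from a higher base (93.2%) and shows a gain of 1.2 points at R² = 0.10, in the same direction. Stable dosing limits change during the trial but does not remove a difference between medicated and unmedicated participants. None of this gives a reason to leave out a stratum that the plan itself chose.

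**Conclusion.** The concern holds, as a small efficiency point in the safe direction. The stratum is absent from every outcome model. The week-12 contrast remains unbiased, type I error is at or below 5%, and planned power is kept. At the planning effect, adjustment gains about 0.2 to 1.1 points of power for R² of 0.02 to 0.05, and 1.7 (blocked) to 2.5 points (not blocked) at R² = 0.10. Below about 0.02 the gain is negligible. These sizes rest on the assumed R², the assumed share medicated and random dropout. The conservative-test result also requires allocation to be balanced within strata, which the documents do not establish. The change is worth making but is not essential to validity.

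**What to change.** In section VI.C, add medication status as recorded at randomisation, and its interaction with time, to the fixed effects of the primary model. State that the secondary, per-protocol and follow-up models carry the same terms. The hypothesis test remains the treatment contrast at week 12. This is appropriate whether or not allocation is blocked. It should be settled before unblinding, since a covariate added later could look data-driven.

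The cost is one phrase, and the variable is already collected for randomisation. If medication status is not prognostic, the lost degree of freedom costs under 0.01 point of power. Without blocking, chance imbalance between arms brings the simulated cost to about 0.3 points (0.906 to 0.902 as rounded).
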